### **1.3 Significance of The Study**

### **a) Nursing Policies**

Standard guidelines and policies for KC implementation among premature infants, thus encouraging collaboration between health care providers and neonatal nurses, are needed. Administrative direction and written declarations are crucial if all parties incorporated in neonatal care are to implement KC with an understanding of their own and others' roles, accountability and responsibilities. The policy should further promote the involvement of all nurses in proper monitoring of the performance of KC and successfully documenting detection of KC implementation by the mother and premature infant against KC. However, the provision of additional nursing staff to ease NICU workloads is not easy, especially because of nursing shortages and the need to make effective use of human resources due to global economic concerns. The development of new approaches to offset bedside teaching and easing the workload of nurses can increase nurses' emphasis on quality neonatal care.

### **b) Nursing practice**

Nurses should encourage mothers to provide KC either in the hospital or in the community setting to improve the quality of health of their premature infants. Education and care should be given to every mother whose infant has LBW because it is premature and she should be encouraged to do KC. Furthermore, KC has demonstrated the advantage of homeostasis compared with standard treatments (incubators, radiator coolers, or open beds). Premature babies receiving KC tend to sustain a stable body temperature and demonstrate improved breathing patterns (Conde-Agudelo, Belizan, Diaz-Rosello, (2014); Christensson, Siles, Moreno, Belaustequi, De La Fuente, Lagercrantz, Puyol, Winberg, (1992); Rojas, Mario, Kaplan, Michael, Quevedo, Maria, Sherwonit, Elaine, Foster, Lauren, Ehrenkranz, Richard, Mayes, Linda, (2003)). Regarding preterm infant hospitalization in general, KC is associated with a reduced risk of infection, serious illness, and mortality.

### **c) Nursing education**

Nurse educators should have the responsibility of increasing the perception, knowledge, practice, and skills of student nurses regarding the kangaroo care technique by arranging in-service education in institutions and also at the hospital level. They should also take active steps to include kangaroo care content in the section on development and growth in neonatal care in the nursing curriculum. Thus, during their practical posting, the students will advocate for mothers in the NICU, hospital, clinic or at the community level to routinely implement KC with their premature infants. This will be recorded in a logbook so the students can achieve the objectives of their posting in an NICU setting in relation to the topic of obstetric, gynaecology, neonatology and paediatric nursing.

Nurse administrators should concentrate on workshops, continuous nursing education(CNE), and in-service education as this will update their perception, knowledge, and practice regarding continuing KC and promoting exclusive breastfeeding. Nurses play a vital role in the care and management of hospitalized preterm infants.

### **d) Mothers and premature infants**

First, early bonding and attachment between a mother and her preterm infant will relieve the mother's physiological and psychological stress. Second, calming practices (holding, touching, talking) and the smell and warmth of the mother's body help to regulate the premature infant's basic behavior, and may contribute to the ability of the infant to control its state. Third, the KC protocol facilitates the individualized attachment between mothers and their preterm infants. Such attachment helps the mother improve her compassion for and reaction to interactive signs from her preterm infant, particularly during feeding.

In addition, the interactions between the mother and her preterm infant are likely to promote growth and development, as well as the recovery and stabilization of the mother's situation by reducing maternal distress, thus fostering the bond between mother and preterm infant.

Finally, breastfeeding after birth motivates and promotes responsive interactions for the maternal and preterm infant bonding attachment. It provides a mother with confidence to take care of her premature infant, increases breast milk supply and is low cost. Practicing KC means a mother's visiting rate is increased and this helps to encourage breastfeeding.

The findings of this study determine that KC, as one of the most relevant nursing interventions, might effectively promote bonding between the mother and preterm infant, as well as foster the growth and development of the infant. The benefits to the premature infant are that it normalizes infant physiology, provides warmth to the baby, promotes lactation, ensures more successful breastfeeding, provides a sense of security to the baby, improves the weight gain of the baby, reduces hospitalization stay, promotes baby-mother bonding and promotes deep sleep in the premature infant.

#### **e) Organization**

Implementing KC will help to reduce the LOS, and fewer infections will occur in the NICU. The organization can cut the purchasing cost of third level antibiotics or other expensive medications required to cure nosocomial infections in the NICU setting. It will also reduce outbreaks in the NICU.

#### **f) Nursing Research**

The KC intervention can be introduced into hospitals all over Malaysia. It is a simple, low cost, and highly effective intervention. Thus, the KC-EP can be provided to nursing students, nurses, and healthcare providers with the purpose of encouraging weight gain, reducing LOS, improving breastfeeding rates, and, therefore, enhancing the quality of neonatal care. A study can also be conducted with a large number of samples in different settings. A similar comparative study can also be conducted including mothers, fathers and other family members with a follow-up at six (6) months old for exclusive breastfeeding assessment.

##### **1.3.3 Missing gaps in the existing literature**

In a previous national survey on aspects of nursing done by Engler, Ludington-Hoe, Cusson, Adams, Bahnsen, Brambaugh, (2002), in relation to perceptions, knowledge, barriers, and practice related to KC, it was indicated that nurses need training resources to address obstacles to KC practice, stressing that knowledge and competence are necessary to reproduce KC securely and efficiently. Such training must also focus on the importance of KC for mothers and preterm infants in order to overcome the lack of knowledge and awareness about KC amongst mothers and nurses in Malaysia in general. Therefore, an intervention study needs to be conducted to evaluate the efficacy of KC-EP to shed light on the mechanisms behind these obstacles for the advantage and efficacy of KC for all preterm infants, mothers and nurses.

In previous studies, only nurses were investigated in terms of perception, knowledge, barriers, and practice. Therefore, it is possible to undertake a comprehensive study of the relevant issues not only for nurses but also for mothers of premature infants in order to determine KC-EP effectiveness.

In previous regional research by UNICEF (2004), during the neonatal period, premature infants with LBW are more prone to develop neonatal morbidities like acute respiratory failure. Those who survive in the neonatal phase tend to be more vulnerable to neonatal morbidity, relative to term infants and those of normal weight, including gastrointestinal disease, respiratory disorders, central nervous system, immunology, vision and hearing (Behrman & Butler 2007). KC will promote evidence-based nursing practice and have various advantages for mothers, premature babies and nurses. The differences between this study and the previous study are that the researchers are evaluating the mother's perspective and premature infant's outcome starting from the day of admission until the infant reaches 3 months old. The researchers also evaluate the nurse's perspective as caregiver in the NICU setting before and after the educational intervention program is conducted.

As stated by Ong (2017), the nurse who is in charge of EBM is concurrently tasked with other administrative tasks due to a shortage of staff as well as the considerable amount of time and limited space to undertake KC. Moreover, the nurses responsible for advocating KC in the unit are also engaged in the work of administrative documentation. There is, therefore, insufficient time available to prepare and advocate for mothers to undertake KC in the unit.

As reported by Chan, Labar, Wallb, and Atuna (2016), these reasons tend to reveal that shortages of staff, staff turnover, lack of knowledge, lack of awareness of the value of KC among nurses generate barriers to implementing kangaroo care within a facility (Seidman et al.,2015).

KC is not the ordinary routine approach in many NICUs in Malaysia. Knowledge and awareness of these techniques among neonatal nurses is still inadequate. This study shows that nursing staff require KC awareness and training to properly understand the effectiveness of KC so it is consistently enforced in the NICU and at home.

Even though over the past three decades, KC has been developed as a safe and effective technique for preterm infant care with the ability to enhance the survival rates of LBW infants, especially in low- and middle-income countries, in Malaysia a structured curriculum for KC, applicable in the local context, has not yet been designed.

This is despite numerous attempts to introduce, educate and train individuals and organizations in a sustainable way to improve coverage of KC. For this reason, KC is often the only available method of caring for premature infants in many developing countries.

In a study by Bergh, Charpak, Ezeonodo & Udani (2012), it was reported that research on KC application, training and education practices and approaches was discussed at an international workshop, and further evidence was gathered from personal experiences, unpublished research presented by colleagues, and published materials. The study provides an illustration of some of the community's core implementing and training issues, and concerns about the

collaborative outcomes. Only nurses' perception, knowledge, barriers, and practice were discussed in the previous studies. The study also suggested a triangular transition change involving transition agents, and the choice of implementation and educational models. The specific positions of the change agents, addressed as drivers, trainers and implementers, were discussed.

KC teaching and training should be strengthened by the same fundamental conceptual definition and should be supported by awareness-raising, dedicated leadership, multidisciplinary collaboration, and ongoing top management support. It should be based on empirical evidence, conducted in line with existing educational best practices, and should be appropriate and applicable locally.

#### **1.4 Research Questions**

KC has gained acceptance as a chosen and effective technique for the quality care of premature infants. However, it is still a new phenomenon in the NICU in Malaysia; also no data has been published regarding the effectiveness of KC in relation to the perception, knowledge and, practices of nurses. In addition, emotional stress also occurs among those mothers whose preterm infants have been admitted to the NICU. This study also explores the outcomes of mothers in terms of their perception, knowledge, barriers and level of stress regarding KC implementation as well as the outcomes for their premature infants; weight gain, LOS and breastfeeding rates associated with compliance with the practice of KC in a Malaysian setting. In view of the lack of literature on a locally contextualized education model for the teaching of kangaroo care, I questioned the need for drafting such an education programme. The main research question of this thesis is;

Can a locally contextualised kangaroo care education programme aimed towards both mothers and NICU nurses be effectively implemented?

To answer the above research question, the following were analysed.

1. Are there any statistically significant changes in mothers' perception, knowledge, perceived barriers regarding KC and their level of stress after participation in a KC-EP between control and experimental groups of mothers at pre-intervention (T0), 1-month post-intervention (T1) and 3-months post-intervention (T2)?
2. Does KC improve premature infants' weight gain, LOS, and breastfeeding rates between a control and an experimental group at pre-intervention (T0), 1-month post-intervention (T1) and 3-months post-intervention (T2)?
3. Are there any statistically significant changes in the nurses' perception, knowledge and practice of KC before and after participation in a KC-EP?

## **1.5 Objectives of The Study**

The general and specific aims of the study are as follows:

### **1.5.1 General Objective**

The general objective of this study was to evaluate the effectiveness of a special KC-EP for mothers', nurses', and premature infants' outcomes in the neonatal intensive care unit (NICU).

### **1.5.2 Specific Objectives**

This study aimed to evaluate a KC-EP supporting KC among mother-infant dyads and nurses.

The specific objectives of this study were to:

1. compare the effectiveness of KC-EP in terms of mothers' perception, knowledge, and perceived barriers regarding KC and their level of stress after participation in a KC-EP between control and experimental groups of mothers at T0, T1 and T2.
2. compare premature infants' weight gain patterns, LOS and breastfeeding rates between control and experimental groups at T0, T1, and T2.

3. compare nurses' perception, knowledge, and practice of KC before and after participation in a KC-EP for nurses.

## **1.6 Hypothesis**

The following hypotheses guided the study:

- $H_1$ : A KC-EP can improve perception, knowledge, and perceived barriers in relation to KC, and levels of stress among mothers.
- $H_2$ : KC is effective in improving weight gain patterns, LOS, and breastfeeding rates among premature infants.
- $H_3$ : A KC-EP can improve nurses' perception, knowledge, and practice in relation to KC implementation.

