***i) Structured Kangaroo Care Educational Program for Mothers (KC-EP)***

The KC-EP for mothers is a special program designed to help preterm infant mothers admitted to the NICU share evidence of the benefits of KC and show them how they can perform KC. There are plenty of online reading and video resources available: blogs, books, magazines, newsletters or newspaper articles, on issues faced by preterm infant mothers admitted to the NICU and how they can reduce maternal stress during separation and improve their neonatal care capabilities related to the NICU. Most of the available materials are general and do not address specific guidelines and practice protocols for performing kangaroo care.

Therefore, a formal content module for mother-infant dyads was developed for the KC-EP. The KC-EP focused on the psychological and physical aspects related to the preparation for and implementation of the KC procedure (before, during, and after). Subsequently, proper handwashing techniques (before and after touching the premature infant) and KCPR booklet documentation were implemented. On the other hand, for interpersonal communication or interaction between mothers and neonatal nurses in the NICU and good relations were established. In addition, mothers were also encouraged to participate in some tasks that were

usually carried out by current ward staff for their premature infants in the NICU, i.e. changing diapers, feeding tube or cup feeding and breastfeeding. In other words, for mothers, the KC-EP was more formal, simplified and based on contextualizing the needs of the regional culture in Malaysia. The positive point is that these short notes, such as flipcharts and leaflets in both languages, could be used to illustrate points for the premature infant mothers and as a quick reference for the neonatal nurses.

This program (KC-EP) had the general objective of ensuring the intervention with the mother-infant dyads was effective and possibly at no cost. The specific aims were to:

- a. Provide mothers with educational information related to KC to ensure the quality of premature infant care at the hospital and after returning home.
- b. Assist mothers in situations, and with facilities, and routine care in the NICU during their premature infant's hospitalization in the NICU.
- c. Develop interpersonal communication and interaction between mothers and neonatal nurses.
- d. Support mothers regarding the psychological aspects of their premature infants.

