### **3.14.5 Telephone call and short message via WhatsApp.**

To ensure continuity of the KC technique and quality of premature infant care, the researchers performed a follow-up through WhatsApp, sending a short message to the mother. This was a reminder about providing updates on the premature infant's performance of KC, the condition of the premature infant; i.e. body weight of preterm infant on discharge, at 1 month and 3 months corrected age, breastfeeding status every 2 weeks post-admission until 40 weeks post-admission. In addition, this continued every 4 weeks at 44 weeks, 48 weeks and 52 weeks of premature infant age [Table 3.2(a) & (b)]. The researchers also made three (3) telephone calls via WhatsApp during the program of which the first call was at 40 weeks post-admission, the second call was at 44 weeks (1 month) post-admission and the last call was at 52 weeks (3 months) post-admission. The purpose of the call was to find out if the mother had any doubts or had any problems linked to the objectives of the study at home and to advise the mother to contact the researcher at any time if she had any problems with KC and her premature infant's condition. All of the conversations were conducted using a very careful approach to ensure that the mothers were openly sharing their feelings and their appreciation of KC.

The program aimed to educate mothers on how to carry out KC and reduce their stress levels and how to strengthen their ability to breastfeed their premature infants. The nurses' workload in the NICU is generally very high, and nurses do not have enough time to assist

the mothers. Therefore, the entire program was allocated only 1 hour and 30 minutes. The experimental group had four sessions prepared and designed for the mothers, the specifics are set out in Appendix L and M. The program was administered in one session with between two (2) or four (4) mothers per group and one or two nurses involved at the first meeting. This was to ensure the nurses and mothers were given the same information , skills and shared attitudes.

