The control group mothers came for visits and saw their preterm infants once a day for 30 minutes to 1 hour, and exercised KC if they were interested. This was the NICU's routine practice. The control group of mothers continued routine ward practice and standard hospital care. Mothers who declined to participate during the time of the study were excluded. For participation in the study, a small token gift was given to (n=48) mother-infant dyads at the control group.

Upon their premature infant's discharge from the hospital, the mothers were reminded to answer the same standardized questionnaire (QI) for T0, T1, and T2. The following posttest questionnaires (Questionnaire I: enclosed in the envelope) were given to the mothers at the NICU or the Pediatrics Clinic on the 1st and 3rd month, when they came for their premature infant's follow-up, and were returned the same day. Consequently, some of the data were collected and sent by email if the mothers could not keep to the time (received on the same day).

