professionals, including two neonatalogists, a nursing professor, a nursing lecturer, and three head nurses who specialized in neonatal nursing. The contents of the KC module were: the meaning of the term KC, benefits of KC, precautions against any abnormality in parameters (temperature, respiratory rate (Sao2), heart rate perfusion (color), and tolerating feeding well in the 24 hours before performing KC. The program included the showing of videos on the KC procedure (standing and sitting transfers). The mothers were prepared with a KC information handout and a leaflet on KC associated with the KCPR. The booklet was developed based on research articles and health-care professional modules on KC in relation to physical, emotional and verbal support, on encouraging mothers to hold their premature infant in the right position for KC and on performing KC for the benefit of their premature infant. KC was started once the preterm infant had been deemed clinically stable. Baby pouches and diapers were provided to all mothers in the experimental group. The researcher developed a personal goal setting self-motivation routine to help mothers achieve the potential best practice of KC for their preterm infants. Self-motivation is a vital part of emotional intelligence and something that is needed by any mother involved in doing KC. It keeps mothers motivated to undertake KC with a minimum period of 1 hour a day during day and night, accumulating to 4 to 5 hours per week. For preterm infants undergoing intravenous fluid therapy, mothers were expected to sit in a comfortable chair near the incubator or cradle of the preterm infant (to facilitate sustained KC).

Data on weight gain (body weight in grams), KC duration in a week (hour/per week), and breastfeeding status (weeks) were collected from T0 to T2. Additionally, the experimental group of mothers maintained documentation of the outcomes of their preterm infant from the day of recruitment until the infant was 3 months old. The diaries provided information on the prospective longitudinal progress outcomes of the premature infants. Each KCPR booklet was labeled as an experimental group progress record and included the identification code

number of the mother-infant dyad. However, if the mother was unable to record the data, she instructed a close family member to help at home.

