1.	Are there any statistically significant differences in mothers' perception, knowledge, perceived barriers regarding KC, and stress related to 'premature infants admission to NICU' after participation in the KC-EP?	Perception, knowledge, perceived barriers and stress related to premature infants' admission to NICU mean scores Effect of KC-EP KC performance (Ordinal data)	Descriptive - mean, SD, skewness and kurtosis Chi-square test, GLM, repeated measure (RM) & Pearson Eta Squared.
2.	Does kangaroo care improve weight gain patterns in premature infants between control and experimental groups at $T_0$ , $T_1$ , and $T_2$ ?	Weight gain patterns (grams) mean score KC compliance Duration (hours/weeks) Frequency and Percentage (Continuous data)	Descriptive – mean, SD, skewness and kurtosis Chi-square test, GLM and t-test.
3.	Does kangaroo care decrease the length of hospitalization stay for premature infants between control and experimental groups?	Length of hospitalization stay Frequency and percentage (Continuous data)	Descriptive – mean, SD, skewness and kurtosis Chi-square test, GLM and test
4.	Does kangaroo care improve breastfeeding rates for premature infants between control and experimental groups?	Breastfeeding rates KC compliance Frequency and percentage (Continuous data)	Descriptive – mean, SD, skewness and kurtosis Chi-square test, GLM and t-test.
5.	Are there any statistically significant differences in nurses' perception, knowledge, and practice regarding KC before and after participation in the KC-EP?	Perception, knowledge, practice mean scores Effect of KC-EP (Ordinal data)	Descriptive - mean, SD, skewness and kurtosis Independent t-test GLM, RM & Pearson Eta Squared.

The key influence of an explanatory variable is its direct effect on the outcome variables (Field, 2011). Additionally, the effects of covariate and covariate interaction with KC can be included in GLM univariate analysis. This covariance analysis is an extension of the variance analysis to include a covariate/confounder component (Field, 2011). This covariance is linearly related to the dependent variable, and its inclusion in the analysis will minimize the error associated with the covariance analysis (Field, 2011). The test is appropriate since

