categorical variables are both independent and dependent variables. Therefore, covariance analysis was used to correct the observed effects on the outcome variables of potential confounders. The summary of the statistical analysis used for all research questions is outlined in Table 3.14. Each of the statistical tests is two-tailed. A p-value below 0.05 was assumed to show statistical significance.

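### H2, research question 2 and Table 3.4 rows 2–4 credit infant outcomes to kangaroo care itself, but the arms compare an education package with earlier usual care in which kangaroo care was allowed

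*Combined protocol and SAP*

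**What the plan says.** H2 (Section 1.6) reads "KC is effective in improving weight gain patterns, LOS, and breastfeeding rates among premature infants". H1 and H3 in the same section are about what a KC-EP can do; only H2 is about KC. Research question 2 (Section 1.4) has the same form as H2, and so do rows 2–4 of Table 3.4 (Section 3.19.1), where row 2 asks "Does kangaroo care improve weight gain patterns in premature infants between control and experimental groups". Section 1.7.2 defines KC for this study narrowly, as a way of holding the infant.

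The title and the general objective (Section 1.5.1) instead evaluate the KC-EP, for infant outcomes as well as for mothers and nurses. Specific objective 2 (Section 1.5.2) only compares the groups.

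- **Control arm.** Section 3.16.1 says control mothers "saw their preterm infants once a day for 30 minutes to 1 hour, and exercised KC if they were interested", as the unit's routine. They had a booklet in which KC could be recorded. Table 3.2 lists breastfeeding support and hand washing for them.
- **Experimental arm.** Section 3.13 lists two sessions, ten messages and three telephone follow-ups. Section 3.14.5 gives as programme aims teaching KC, reducing stress and "how to strengthen their ability to breastfeed their premature infants". Under the programme description in Section 3.11, "mothers were also encouraged to participate in some tasks that were" normally done by ward staff, including feeding and diaper changes. Section 3.16.2 adds that "Baby pouches and diapers were provided to all mothers in the experimental group". Recruitment followed the nurses' programme, which was meant to have nurses promote KC and breastfeeding (Section 3.15.3).

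**The concern.** The infant hypotheses name one cause, and the comparison varies several things at once. Two problems follow, and they work in opposite directions.

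- **Package.** Coaching on breastfeeding, practice in care tasks, repeated contact and trained nurses can influence infant outcomes by routes other than skin-to-skin holding. Breastfeeding is a direct programme aim. Section 2.3.7 makes sucking, weight and the mother's confidence part of the discharge criteria, so length of stay (LOS) could also move. A difference between arms could then be reported as a KC effect that was not there.
- **Control-arm KC.** If some control mothers do KC, a real KC effect is diluted, and a null result could be reported as KC not working.

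Weight gain and LOS are the primary infant outcomes (Section 3.9), so the trial's main infant conclusion is affected.

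**Working it through.** **1. Which statements name which cause**

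| Place | What is evaluated |
|---|---|
| Title; Section 1.5.1 | KC-EP |
| Section 1.5.2, objective 2 | Difference between groups, no cause named |
| Section 1.6, H1 and H3 | KC-EP |
| Section 1.6, H2; Section 1.4, question 2; Table 3.4 rows 2–4 | KC |

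**2. What differs between the arms**

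| Element | Control | Experimental |
|---|---|---|
| KC | Optional, uptake not stated | Taught and encouraged |
| Breastfeeding | Support, with mothers attended when they ask | Structured education and follow-up |
| Stress and care tasks | Routine care | Programme content |
| Messages and calls | None listed | Ten and three (Section 3.13) |
| Nurses | Before the KC-EP for nurses | After it |
| Period | February–July 2018 | Later, to April 2019 |

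The contrast is therefore the package after nurse training against earlier usual care with KC allowed.

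**3. Does any planned analysis separate KC from the rest?** KC hours are recorded (Section 3.16.4) and banded (Section 3.20.1). Table 3.4 lists KC compliance in rows 2 and 4, but not in row 3 (LOS). Section 3.19.1 permits covariates in general terms. No model of infant outcome by KC amount is specified. Any such model would be observational, because mothers choose their hours.

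**4. The plan's own sample size.** Inputs from Section 3.7.2 are a difference of 0.54, SD 0.8, and z-values 1.96 and 0.842. Section 3.19.1 adds "Each of the statistical tests is two-tailed" and "A p-value below 0.05 was assumed to show statistical significance".

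n = 2 × (1.96 + 0.842)² × 0.8² / 0.54² = 34.5, so 35 per group. The plan's rounded denominator of 0.29 gives 34.65, also 35. Then 35 / (1 − 0.30) = 50. Both stated figures reproduce. With the 48 per group in Section 3.7.2, SE = 0.8 × √(2/48) = 0.163 and power = Φ(0.54/0.163 − 1.96) ≈ 91%. The section also cites a difference of 8.41 without explaining the change to 0.54; I use 0.54 because the formula does.

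**5. Illustration: dilution by control-arm KC.** Assume every experimental mother does KC, a proportion c of controls does, and the effect is proportional to the difference in uptake. The contrast is 0.54 × (1 − c).

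| c | Contrast | Power at 48 per group | n per group for 80% power |
|---|---|---|---|
| 0% | 0.54 | 91% | 35 |
| 10% | 0.49 | 85% | 43 |
| 30% | 0.38 | 64% | 71 |
| 50% | 0.27 | 38% | 138 |

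**6. Illustration: a package or period effect with no KC effect.** For a non-KC difference s, the chance of a significant result is Φ(s/0.163 − 1.96) + Φ(−s/0.163 − 1.96). For s = 0.1, 0.2, 0.3, 0.4 and 0.54 this is 9, 23, 45, 69 and 91%. H2 would read each such result as KC being effective.

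The documents give neither c nor s. Both tables show sensitivity and are not estimates.

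**The case against.** The best defence is that H2 is shorthand. The title, general objective and main research question are already at programme level, and Section 1.7.1 describes effectiveness as outcomes before and after KC is implemented. This stands as far as it goes: the fault lies in inconsistent wording, and the plan as a whole does not aim at KC alone. It does not rescue H2, because H1 and H3 name the programme where H2 does not, and Section 1.7.2 defines KC as a holding technique.

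Several stronger readings are tempting and are not supported:

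- **That controls had no breastfeeding help.** Table 3.2 lists support, and Section 3.16.4 describes routine discharge advice to continue breastfeeding. The difference is one of structure and intensity.
- **That every package element is a rival cause.** Pouches and diapers are mainly aids to KC. Much of the messaging serves KC continuity and is a means of delivering it.
- **That control KC matched the experimental target.** Daily visits of 0.5–1 h come to 7 × 0.5 = 3.5 to 7 × 1 = 7 h a week, which spans the 4–5 h sought in the experimental arm. That is a ceiling, because it treats whole visits as KC. Section 2.5.2 says KC is not widely practised in this setting, and the training slides in Appendix P credit no physiological benefit to under 30 minutes a day.
- **That uptake of 25–50% in controls can be presumed.** Nothing in the documents supports that range. At 10% uptake, power falls only from 91% to 85%.
- **That KC exposure is ignored.** Rows 2 and 4 of Table 3.4 already list compliance.

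**Conclusion.** The concern holds as one of attribution. The comparison cannot support a statement that KC is, or is not, effective for weight gain, LOS or breastfeeding, because KC is neither absent from the control arm nor the only thing added in the experimental arm, and no planned analysis separates them. The package problem carries more weight than dilution, since control uptake was probably low.

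The size is unknown. The 91, 85, 64 and 38% power figures rest on the plan's 0.54 and 0.8, 48 per group, full experimental uptake and an effect proportional to uptake.

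A reader might infer that naming the programme instead of KC would make the claim causal. It would not. The arms were recruited in sequence and non-randomly (Sections 3.7.2, 3.16 and 3.16.2), so the package is confounded with calendar time. The most the comparison supports is an association with the package.

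**What to change.** 1. Reword H2, research question 2 and Table 3.4 rows 2–4 to the contrast made: *KC-EP delivered after nurse training versus earlier usual NICU care in which KC was allowed*.
2. Extend the compliance entry in rows 2 and 4 to a table of KC hours per week by arm, using the six bands in Section 3.20.1, and show it beside every infant outcome, including LOS.
3. Label any analysis of outcome by KC hours as exploratory and non-causal.
4. Limit the infant conclusion to an association with the programme package, and state that allocation was sequential and non-random.

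The cost is the wording of one hypothesis, one research question and three table rows, plus one descriptive table from booklet data already collected. Sample size, endpoints and tests do not change. The downside is a narrower claim about KC.
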